### **18.3. PREGNANCY TESTING**

A serum pregnancy test is performed on all females of childbearing potential (FOCBP) at the teduglutide pre-treatment visit (when the pre-treatment and screening visits are combined, the serum pregnancy test should be performed at the local laboratory). Urine pregnancy tests will be administrated at all other visits according to the study schedules. The pregnancy test result (Positive, Negative) will be presented in a listing.

### **18.4. ANTIBODIES TO TEDUGLUTIDE**

Blood samples for antibodies will be drawn for all the teduglutide-exposed subjects. The sample drawn on CxD1 must be drawn prior to administration of the first dose of teduglutide. Once the subject has started teduglutide treatment (CxW12 and CxW24), samples must be drawn at least 14 hours after dosing. Subjects who test positive for antibodies to teduglutide will also be tested for neutralizing antibody. Subjects who have been previously treated with teduglutide, and who test positive for antibodies to teduglutide, will have follow-up blood draws for antibodies to teduglutide every 12 weeks while on study until a negative result is

---

Document: \\quintiles.net\Enterprise\Apps\sasdata\SASa\sas\Shire\Teduglutide\ZXA48914\Biostatistics\Documentation\SAP\SHP633-303\_SAP\_Draft\_V1.0\_20171023

Author: [REDACTED] Version Number: Draft V1.2  
Version Date: 16Jan2018

Template No: CS\_TP\_BS016 – Revision 3  
Effective Date: 01May2012

Reference: CS\_WI\_BS005

Copyright © 2012 Quintiles Transnational Corp. All rights reserved.  
The contents of this document are confidential and proprietary to Quintiles Transnational Corp. Unauthorized use, disclosure or reproduction is strictly prohibited.

obtained.

The number and percent of subjects with an antibody finding (Antibodies to Teduglutide Negative/Positive, Neutralizing Antibodies Present/ No Neutralizing Antibodies Present) will be summarized at CxD1, CxW12, CxW24, CxW28 and EOS. Non-specific antibodies will be categorized as Negative.

The follow-up antibody assessments after study completion will not be transferred from the lab vendor for any statistical analysis.

### **18.5. GASTROINTESTINAL-SPECIFIC TESTING**

Fecal occult blood testing (FOBT) must be performed on all subjects at the pre-treatment visit (Px), CxW12, and CxW24 of the teduglutide cycle. During NTT periods, FOBT must be performed on teduglutide-exposed subjects (subjects who have received teduglutide any time in the past and are therefore not teduglutide-naïve) on a roughly annual basis (approximately every 48-60 weeks). The colonoscopy or sigmoidoscopy will be performed in response to positive FOBTs.

GI-specific testing will be summarized for the teduglutide treatment cycles only. The clinically significant abnormal results will be presented in a data listing. Fecal occult blood testing will be summarized as 'Negative', 'Positive, not clinically significant', 'Positive, clinically significant'. The results of colonoscopy or sigmoidoscopy will be reported as 'Normal', 'Abnormal, not clinically significant', or 'Abnormal, clinically significant'. All FOBT, along with subsequent colonoscopy or sigmoidoscopy testing, will be presented in an appendix listing.

### **18.6. PHYSICAL EXAMINATION**

Physical examination dates and reason that an examination was not done will be presented in data listings. Any clinically significant findings for physical examination are recorded as adverse events.

### **18.7. VITAL SIGNS**

The following vital signs measurements will be reported for this study:

- Systolic Blood Pressure (mmHg)
- Diastolic Blood Pressure (mmHg)

Document: \\quintiles.net\Enterprise\Apps\sasdata\SASa\sas\Shire\Teduglutide\ZXA48914\Biostatistics\Documentation\SAP\SHP633-303\_SAP\_Draft\_V1.0\_20171023

Author: [REDACTED]

Version Number:  
Version Date:

Draft V1.2  
16Jan2018

Template No: CS\_TP\_BS016 – Revision 3  
Effective Date: 01May2012

Reference: CS\_WI\_BS005

Copyright © 2012 Quintiles Transnational Corp. All rights reserved.  
The contents of this document are confidential and proprietary to Quintiles Transnational Corp. Unauthorized use, disclosure or reproduction is strictly prohibited.

- Pulse Rate (bpm)
- Temperature (°C)
- Weight (kg)
- Height or length (cm)

The following vital signs parameters will be derived for this study:

- BMI (kg/m^2)
- Height Z-score
- Weight Z-score
- BMI Z-score

Descriptive statistics will be used to summarize vital signs measurements and derived BMI in actual value and change from baseline for each treatment group by age group (<1, 1-<12, 12-<17, 17-<18 years and overall) at study site visits where associated parameters are collected. Z-scores of vital signs by site visits will also be summarized and presented in Mean ± SE Plot. A listing will also be provided.

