#### **14.2. GROWTH DATA**

The last representative value for height and weight during each 12-week interval throughout the retrospective observation period will be captured in the Growth Data (Retrospective Period) form of eCRF as well as the head circumference for subjects 36 months of age and younger at the time the data was collected.

Document: \\quintiles.net\Enterprise\Apps\sasdata\SASa\sas\Shire\Teduglutide\ZXA48914\Biostatistics\Documentation\Protocol\SHP633-303\_Retrospective\_SAP\_Final\_V1.0\_20171013  
Author: [REDACTED] Version Number: Final V1.0  
Version Date: 13Oct2017

Template No: CS\_TP\_BS016 – Revision 3  
Effective Date: 01May2012

Reference: CS\_WI\_BS005

Copyright © 2012 Quintiles Transnational Corp. All rights reserved.  
The contents of this document are confidential and proprietary to Quintiles Transnational Corp. Unauthorized use, disclosure or reproduction is strictly prohibited.

The following growth data will be reported for retrospective observation period:

- Height (cm)
- Weight (kg)
- Head circumference (cm) for subjects  $\leq$  36 months of age

The following parameters will be derived during each 12-week interval:

- BMI ( $\text{kg}/\text{m}^2$ ) [when both height and weight are available in the interval]
- Height Z-score
- Weight Z-score
- BMI Z-score
- Head circumference Z-score for subjects  $\leq$  36 months of age

Descriptive statistics will be used to summarize growth data and derived parameters in actual value and change from baseline at 12-week intervals where associated parameters are collected. A mean  $\pm$  SE plot and a data listing will also be provided.

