## 7.2. BASELINE

Unless otherwise specified, baseline is defined as the last non-missing measurement on or prior to baseline visit in the core study TED-C13-003.

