## 7.4. STUDY CYCLE CONVENTIONS

Visits will be summarized within the associated pretreatment period or treatment cycle or no treatment period. For teduglutide treatment cycles, Cycle x Day 1, Cycle x Week 1, ..., Cycle x Week 24, Cycle x Week 25 Follow-up, Cycle x Week 26 Follow-up, Cycle x Week 27 Follow-up and Cycle x Week 28 data will be collected according to the schedule of events.

For NTT periods, NTx data will be collected approximately every 12 weeks. Data for teduglutide treatment periods and NTT periods will be presented in separate tables.

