## 7.7. COMMON CALCULATIONS

For quantitative measurements, change from baseline will be calculated as:

Test Value at Visit X – Baseline Value

Percent change from baseline will be calculated as:

(Test Value at Visit X – Baseline Value) / Baseline Value \*100

Change (or percent change) from baseline tables will be calculated based on the number of subjects in the treatment group with a non-missing value at baseline and at the time point being analyzed.

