## **11. DEMOGRAPHIC AND OTHER BASELINE CHARACTERISTICS**

Demographic data and other baseline characteristics will be presented.

The following demographic and other baseline characteristics will be summarized:

- Age (years) at baseline of TED-C13-003
- Age Group – Age is categorized in pre-defined groups: < 1, 1 to <12, 12 to <17, 17 to <18.
- Sex (if female, the reproductive status will be reported)
- Race
- Ethnicity
- Weight Z-score at baseline of TED-C13-003
- Height Z-score at baseline of TED-C13-003
- Body Mass Index (BMI) Z-score at baseline of TED-C13-003

---

Document: \\quintiles.net\Enterprise\Apps\sasdata\SASa\sas\Shire\Teduglutide\ZXA48914\Biostatistics\Documentation\SAP\SHP633-303\_SAP\_Draft\_V1.0\_20171023

Author: [REDACTED]

Version Number:  
Version Date:

Draft V1.2  
16Jan2018

Template No: CS\_TP\_BS016 – Revision 3  
Effective Date: 01May2012

Reference: CS\_WI\_BS005

Copyright © 2012 Quintiles Transnational Corp. All rights reserved.  
The contents of this document are confidential and proprietary to Quintiles Transnational Corp. Unauthorized use, disclosure or reproduction is strictly prohibited.

The demographic data collected in the study eCRF will be listed by subject.

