## APPENDIX 1. PROGRAMMING CONVENTIONS FOR OUTPUTS

### SHIRE OUTPUT STANDARDS – TFLs4SHIREFINALV6.0

Outputs will be presented according to Shire output standards document TFLs4ShireFinalV6.0.

General considerations which are applicable to the study are summarized as following:

- **Statistics Presentation**

For the by-time-point tables, the number of subjects at each timepoint (n) represents the number that had a valid result for a given parameter at that timepoint.

The default summary statistics presented in the TFLs4Shire table shells for continuous variables include n, mean, standard deviation, median, minimum, and maximum. For categorical variables, the count (n) and percent (%) are the default statistics; unless otherwise stated or the associated number of subjects for the corresponding time point is provided, the denominator for percentages is N (the number of subjects in the treatment group/analysis set). Note that for any summary by subgroups (e.g., by sex), the denominator is the number of subjects in that subgroup/treatment group/analysis set. For most safety tables, the study teams should use the default statistics; the study team should carefully consider and give sufficient justification prior to requesting the use of other summary statistics. Percentages will be reported to 1 decimal place, except when the percentage equals exactly 100 where it will be displayed as an integer (100). For zero, only count and no percentage will be displayed.

- **Alignment**

Output should be aligned so that in the body of the table, where applicable, text is left-justified within a cell, stats output is aligned centrally within a cell and lined up by decimal point.

Handling of missing values: In listings, missing values for numerical data will be reported as a period “.” and missing values for character data as a blank “ ”. In the summary tables for categorical data, “Missing” will always be displayed as a category to represent missing data, where applicable. The default denominator will be all subjects in the analysis set unless otherwise specified in the SAP. For both tables and listings where there are no observations (and hence there would be no output), the table/listing should be produced with all titles and footnotes as per its shell, but with the text showing no observations in the body of the output.

- **Decimal Places and Rounding Rules**

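### Prospective SAP section 18.7 gives change from baseline for raw weight, height and BMI but not for their Z-scores, so mild to moderate growth faltering can be obscured

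*SAP*

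**What the plan says.** Section 18.7 of the prospective SAP lists weight and height among the measurements. Its derived parameters are BMI and the height, weight and BMI Z-scores. The analysis is then given in two sentences. The first reads "Descriptive statistics will be used to summarize vital signs measurements and derived BMI in actual value and change from baseline for each treatment group", with a split by age group. The second reads "Z-scores of vital signs by site visits will also be summarized and presented in Mean ± SE Plot". Of the four derived parameters, only BMI is named in the sentence that specifies change.

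Section 14.2 of the retrospective SAP has the same kind of derived list, Z-scores included, and states "Descriptive statistics will be used to summarize growth data and derived parameters in actual value and change from baseline at 12-week intervals".

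Four other parts of the prospective SAP matter here:
- Section 7.7 makes change tables paired: they are "based on the number of subjects in the treatment group with a non-missing value at baseline and at the time point being analyzed".
- Appendix 1 makes by-visit tables unpaired: "the number of subjects at each timepoint (n) represents the number that had a valid result for a given parameter at that timepoint".
- Section 7.4 splits the visits further: "Data for teduglutide treatment periods and NTT periods will be presented in separate tables".
- Section 7.2 sets the reference point: "baseline is defined as the last non-missing measurement on or prior to baseline visit in the core study TED-C13-003".

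**The concern.** Parenteral support is being reduced in these children, in some cases to nothing. Whether each child holds its own growth trajectory meanwhile is a safety question, and long-term safety is the primary objective (section 3.1). The Z-score is the scale that answers it, because it removes the growth expected for age and sex.

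As written, the paired analysis is on the wrong scale and the right scale is unpaired. Raw change from the core-study baseline mixes faltering with expected growth over an interval that differs between children. The age bands do not cure this, since one of them runs from 1 to under 12 years. Mean Z-score by visit is age-standardised but averages over whoever contributes. Children enter treatment cycles on eligibility criteria and can leave follow-up early for clinical deterioration (section 4.1), so the contributors need not be alike from visit to visit. A mean Z-score can then move without any child changing, or stay level while every child falls.

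**Working it through.** The plan states no figure to reproduce. The check is a reading of the text followed by two illustrations, and every growth value in them is an assumption.

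**Text.** No other section of the prospective SAP adds a change analysis for Z-scores. Section 7.7 defines how change is computed, not which variables receive it. Section 11 summarises the baseline values once (for example "Height Z-score at baseline of TED-C13-003"), and section 18.7.1 derives the visit values.

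**Raw height change while the Z-score falls.** The formula in section 18.7.1 with L = 1 gives height = M(1 + S·Z). Starting at Z = -1.5 with Z-score change d:

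raw change = M1·[1 + S·(-1.5 + d)] - M0·[1 + S·(-1.5)]

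- Case 1: M0 = 87 cm, M1 = 102 cm, S = 0.04. Baseline is 87 × 0.94 = 81.78 cm. With d = 0, follow-up is 102 × 0.94 = 95.88 cm. Each unit of Z lost costs 102 × 0.04 = 4.08 cm.
- Case 2: M0 = 135 cm, M1 = 145 cm, S = 0.045. Baseline is 135 × 0.9325 = 125.89 cm. With d = 0, follow-up is 145 × 0.9325 = 135.21 cm. Each unit of Z lost costs 145 × 0.045 = 6.525 cm.

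| Z-score change d | Case 1 (cm) | Case 2 (cm) |
|---|---|---|
| 0 | +14.1 | +9.3 |
| -0.25 | +13.1 | +7.7 |
| -0.5 | +12.1 | +6.1 |
| -1.0 | +10.0 | +2.8 |
| d at which raw change is zero | about -3.5 (14.10 / 4.08) | about -1.4 (9.325 / 6.525) |

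Weight behaves the same way. With M rising from 19 to 24 kg, S = 0.15 and starting Z = -1, the raw gain is 4.3, 3.4, 2.5 and 0.7 kg for the same four values of d.

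**Change in who contributes.** Take 20 children with mean baseline Z = -1.0, each truly falling by 0.30. Later, k are absent, with mean baseline Z of Za.

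mean baseline Z of those remaining = [20 × (-1.0) - k·Za] / (20 - k)

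apparent change = that mean - 0.30 + 1.0

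For k = 5 and Za = -2.0: (-20 + 10)/15 = -0.667, so the apparent change is +0.03. For k = 5 and Za = 0: -20/15 = -1.333, giving -0.63.

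| Absent | Za = -2.0 | Za = -1.0 | Za = 0.0 | Paired change |
|---|---|---|---|---|
| 3 | -0.12 | -0.30 | -0.48 | -0.30 |
| 5 | +0.03 | -0.30 | -0.63 | -0.30 |
| 8 | +0.37 | -0.30 | -0.97 | -0.30 |

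The paired column is constant because an equal fall in every child was assumed.

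**Simulation without that assumption.** It used 40 children, Z-score SD 1, correlation 0.9 between baseline and later Z, and 50% or 70% contributing later. If contribution is unrelated to baseline Z, the visit means recover the true fall. If children with higher baseline Z tend to remain, a true -0.25 appears as -0.05 to +0.25 and a true -0.50 as -0.31 to -0.01. The paired summary gives -0.25 to -0.30 and -0.50 to -0.56 across all scenarios.

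**The case against.** The best counter-reading is that section 18.7 does not exclude change for Z-scores. They are already age-standardised, so the separate sentence may only drop the age-group split and add the plot. The shells are in a separate file and may already include the column. This is a fair limit. Still, the text does not specify the analysis, and singling out BMI from the derived list points the other way.

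Second, Z-scores are not hidden. They are tabulated by visit with n, plotted, and summarised at baseline, and a listing is planned. With about 40 children expected, individual courses can be followed if the listing carries Z-scores. Severe faltering would also show in raw change. This stands, and it is why the claim is confined to mild to moderate loss.

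Third, the ends of the composition table need strong selection. At a Z-score SD of 1, the lowest 8 of 20 children lie on average about 0.93 below the mean, so the +0.37 entry is slightly beyond perfect selection. The +0.03 entry needs about 82% of the maximum (1.0 of 1.21). At half-maximal selection a true -0.30 appears as about -0.17, -0.10 and +0.01 for 3, 5 and 8 absent; at a quarter, as -0.24, -0.20 and -0.15. The extremes should therefore be read as bounds, but the fall is still understated under moderate selection. The SAP does not say that attendance depends on baseline Z.

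Finally, two separate SAPs need not share a layout, and the analysis is descriptive with no tests. True, but a descriptive safety summary should still use the scale and pairing that answer its question.

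**Conclusion.** The concern holds. Followed as written, the prospective analysis has no stated paired change on the age-standardised growth scale, whereas the retrospective analysis does. On the assumed values, a height Z-score loss of 0.5 coexists with a raw gain of 6 to 12 cm, and an unpaired mean Z-score can understate, cancel or exaggerate a true fall of 0.30 depending on who contributes. These sizes rest on assumed medians, coefficients of variation and patterns of absence. If the same children contribute throughout, or absence is unrelated to baseline Z, the visit means are not biased. Paired change is not a full remedy, because selective dropout could still bias it. It does show the average within-child shift among contributors directly. This is a worthwhile correction to a safety summary and invalidates nothing else in the plan. Confidence is moderate because the shells were not available.

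**What to change.** In section 18.7 of the prospective SAP, state that height, weight and BMI Z-scores are summarised by visit, within treatment cycle and NTT period, both as actual value and as within-subject change from core-study baseline, with the paired n shown, as in section 14.2 of the retrospective SAP. Change from Cycle x Day 1 and a plot of Z-score change are optional additions.

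The cost is one sentence and one table column. No new data or derivation is needed, and the prospective SAP is still at Draft V1.2. If the shells already include the column, the edit only brings the text into line with them.

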#### 18.7.1. VITAL SIGNS SPECIFIC DERIVATIONS

- BMI

BMI = 10000\* Body weight (kg)/body height (cm), where both body weight and body height data are available at the same scheduled visit

- Height, Weight and BMI Z-scores

Official and validated SAS programs created by Centers for Disease Control and Prevention (CDC) will be used to calculate the Z-scores (standard deviations) for a child's sex and age (up to 20 years of age) for BMI, weight, and height based on the CDC growth charts for children age 2 years and older and the WHO growth charts for infants and children < 2 years of age. For more information on the CDC SAS programs, see [http://www.cdc.gov/growthcharts/computer\\_programs.htm](http://www.cdc.gov/growthcharts/computer_programs.htm).

Z-scores are calculated as the formula below:

$$\text{Z-score} = [((\text{observed value} / M) ^ L) - 1] / (S * L)$$

In which 'observed value' is the child's height, weight or derived BMI. The L, M, and S values vary according to the child's sex and age. For more information on the LMS

Document: \\quintiles.net\Enterprise\Apps\sasdata\SASa\sas\Shire\Teduglutide\ZXA48914\Biostatistics\Documentation\SAP\SHP633-303\_SAP\_Draft\_V1.0\_20171023

Author: [REDACTED]

Version Number:

Draft V1.2

Version Date:

16Jan2018

Template No: CS\_TP\_BS016 – Revision 3

Reference: CS\_WI\_BS005

Effective Date: 01May2012

Copyright © 2012 Quintiles Transnational Corp. All rights reserved.

The contents of this document are confidential and proprietary to Quintiles Transnational Corp. Unauthorized use, disclosure or reproduction is strictly prohibited.

method, see <http://www.ncbi.nlm.nih.gov/pmc/articles/PMC27365/>.

## 18.8. FECAL AND URINE OUTPUT

Urine and stool output data is recorded over a 48-hour period of PS stability before every scheduled site visit and within 1 week of implementing any PS adjustment.

The average daily urine output (mL/kg/day) at the scheduled site visit will be calculated as follows:

(Total urine output over 48 hours / 2) / body weight (kg) at the scheduled visit

where total urine output is calculated as the sum of the urine output in mL and the urine-only diaper weights in g (1g = 1mL) for the subject collected on the output diary form of eCRF. Values will not be calculated if the urine output is not available at the visit. If the body weight at the scheduled visit is missing, the last available weight assessment will be used.

The average daily fecal output will be summarized separately by the average number of stools per day, the average typical stool form score using Bristol Stool Form Scale, the average total daily stool/mixed stool diaper weight (g/kg/day) and the average ostomy output per day (mL/kg/day) for each visit. The average number of stools per day and the average typical stool form score will be calculated as (sum of the daily data in a 48-hour period / 2). The body weight will be used to calculate the daily stool/mixed stool diaper weight (g/kg/day) and the total ostomy output per day (mL/kg/day) using the same formula as for the average daily urine output.

For outcomes where baseline values are available, the change in average daily output for fecal and urine output from baseline to each scheduled visit of treatment periods, as well as at 12-week intervals of NTx, will be presented by treatment group using descriptive statistics. A listing will also be provided.

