### **8.3. MISSING DATA**

Missing data will in general not be imputed. However, partial dates will contribute to the analysis as described in Appendix 2. All available data will be included in the safety analysis.

Details for the imputation algorithm for the missing endpoint values for PS parameters (volume, calories and etc.) will be described in Section [16.1.1](#) of this analysis plan.

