### 16.1. EFFICACY ENDPOINTS

#### 16.1.1. EFFICACY VARIABLES & DERIVATIONS

The efficacy endpoints will be analyzed in two ways: 1) based on the subject diary data (also referred to as "actual"), and 2) based on the investigator-prescribed data (referred to as "prescribed"). PS will be reported in both subject diary data and the investigator-prescribed data in the eCRF. Investigator-prescribed data are the most recent PS prescription (prescription adjustments) prior to or on the date of visit, captured in the PS adjustments eCRFs. Data collected include prescribed weekly total kilocalories, volume, number of days per week, and average hours per day. PS diary data are collected 2 weeks prior to all scheduled site visits (except at pre-treatment visit) in the Intake Diary eCRFs over 24-hour periods that start on the assigned date. Depending on the time of day at which the 24 hour period begins, which can vary by subject, overnight PS volumes after midnight may be associated with prior the date. Data collected include actual PS total infusion duration, total volume and total kilocalories on the assigned date.

The calculation of average daily prescribed PS volume/caloric intake normalized to weight will follow the formula below:

Average daily value = (prescribed weekly PS parameter / 7) / last available weight prior to or on the date of visit.

The calculation of average daily actual PS will be based on the daily support recorded in

Document: \\quintiles.net\Enterprise\Apps\sasdata\SASa\sas\Shire\Teduglutide\ZXA48914\Biostatistics\Documentation\SAP\SHP633-303\_SAP\_Draft\_V1.0\_20171023

Author: [REDACTED] Version Number: Draft V1.2  
Version Date: 16Jan2018

Template No: CS\_TP\_BS016 – Revision 3  
Effective Date: 01May2012

Reference: CS\_WI\_BS005

Copyright © 2012 Quintiles Transnational Corp. All rights reserved.  
The contents of this document are confidential and proprietary to Quintiles Transnational Corp. Unauthorized use, disclosure or reproduction is strictly prohibited.

subjects' diaries within 7 days prior to the date of each scheduled visit. If more than 2 days' values in a week are missing, the average daily value will not be calculated and will be assigned as missing. The same strategy will be used to calculate all other average diary parameters. The calculation of actual PS volume normalized to weight will follow the formula below:

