Average daily value = [(sum of non-missing actual daily values in the diary / number of days with non-missing values)] / last available body weight prior to the visit

Baseline actual PS will be calculated using all the diary data collected within 14 days prior to the first dose or baseline visit of the core study. If more than 5 days' values are missing in two weeks before the baseline visit the core study, the baseline values are missing.

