#### 16.1.1.4. Change and percent change from baseline in hours per day and days per week of PS

Change and percent change in hours per day and days per week of PS from baseline to each study visit will be summarized.

Hours per day of actual PS for all visits except the baseline visit will be calculated as follows:

Hours per day of actual PS = (sum of hours per day for each day that PS intake data is recorded within the 7 days prior to the visit / number of days that PS hours per day data is recorded within the 7 days prior to the visit)

Days per week of actual PS for all visits except the baseline visit will be calculated as follows:

Days per week of actual PS = (number of days with non-zero values for PS volume within the 7 days prior to the visit / number of days for which any PS intake data is recorded within the 7 days prior to the visit) \* 7

Prescribed PS hours per day and days per week for each visit (including baseline) will be taken from the most recent prescription data prior to or at that visit.

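### Prospective SAP 18.8 divides the stool form score by a fixed 2, which suits a count but not a rating: a visit with only one rated day is either halved or lost

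*SAP*

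**What the plan says.** Section 18.8 of the prospective SAP (Fecal and Urine Output) collects urine and stool data over 48 hours before each scheduled site visit. Fecal output is summarized by visit through several measures, two of which share one formula: the number of stools per day and the typical stool form on the Bristol scale. For the second, the text reads "average typical stool form score will be calculated as (sum of the daily data in a 48-hour period / 2").

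The only rule in 18.8 for absent output concerns urine: "Values will not be calculated if the urine output is not available at the visit". The section then plans a change table: "For outcomes where baseline values are available, the change in average daily output for fecal and urine output from baseline to each scheduled visit".

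Three other places bear on the question.

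- Section 8.3 declines in general to impute and adds: "All available data will be included in the safety analysis".
- Section 16.1.1, for PS diary data, says that if more than 2 days' "values in a week are missing, the average daily value will not be calculated and will be assigned as missing". It then extends this strategy to the other averages taken from diaries. Its formula for actual PS uses "sum of non-missing actual daily values in the diary / number of days with non-missing values".
- Section 16.1.1.4 divides hours per day of PS by the "number of days that PS hours per day data is recorded within the 7 days prior to the visit".

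**The concern.** A count and a rating behave differently on a day without stool. For the count, the day contributes a genuine 0 and belongs in the divisor. For the rating, there is nothing to score, so the day adds nothing to the sum but still sits in a divisor fixed at 2. This can happen with a fully completed diary, so it is not only a question of missing data.

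If the formula is programmed on the available ratings, the resulting half-score looks like any other result. Appendix 1 of the prospective SAP says that n at each time point "represents the number that had a valid result for a given parameter at that timepoint", so the visit is counted. It enters the by-visit summary and, where a baseline exists, the change from baseline. The form score then depends partly on stool frequency: a subject whose stools become rarer could show a lower form score with no change in form.

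**Working it through.** The plan states no numerical result on this point, so there is no figure to reproduce. The check compares the formula in 18.8 with a mean over rated days. The ratings are examples, not data.

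**Single visit**

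| Ratings in the 48 hours | Sum of available ratings / 2 | Sum / number of rated days |
|---|---|---|
| 6 and 6 | 12/2 = 6.0 | 12/2 = 6.0 |
| 6 and none | 6/2 = 3.0 | 6/1 = 6.0 |
| 3 and 3 | 6/2 = 3.0 | 6/2 = 3.0 |

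With two ratings the formula is correct. With one, it returns exactly half, and the second and third rows cannot be told apart. For the stool count, 3 stools and then a documented 0 give 3/2 = 1.5, which is right.

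**Change from baseline with unchanged form.** Baseline 6 and 6, visit 6 and none: 3.0 − 6.0 = −3.0 by the fixed divisor; 6.0 − 6.0 = 0.0 over rated days.

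**Group mean.** Let q be the share of visits with one rating and m the true mean at those visits. Halving them shifts the overall mean by q × (m/2 − m) = −m × q/2, whatever the number of subjects. The documents give neither m nor q, so the following values are assumptions that only show the scale:

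| q | m = 4 | m = 6 |
|---|---|---|
| 5% | −0.10 | −0.15 |
| 10% | −0.20 | −0.30 |
| 30% | −0.60 | −0.90 |

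**The other reading.** If a two-day sum with one absent rating is undefined, no score is halved, but the share q of visits drops out of the summary.

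**Does another rule decide?**

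- The availability rule in 18.8 names urine output only.
- The 16.1.1 threshold needs more than 2 missing days. A 48-hour diary has 2 days, so the threshold can never be reached.
- The 16.1.1 formula for actual PS would divide by the days with values, giving 6/1 = 6.0. That is a different divisor from the explicit 2 in 18.8.
- Section 8.3 pulls both ways. Not imputing counts against letting an absent rating act as 0; keeping all available data counts against dropping the day that was rated.

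**The case against.** The strongest case against the point has three parts.

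First, 16.1.1 extends its missing-day strategy to the other diary averages, and 18.8 takes its urine data from an output diary form. If that strategy brings the non-missing-day divisor with it, the SAP already gives the sensible answer. This deserves weight, and it would be wrong to say that nothing else in the SAP touches the case. But the strategy is a 7-day rule placed in the PS derivations, and borrowing its divisor contradicts the explicit division by 2 in 18.8. The two sections would still need reconciling.

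Second, a reader might infer that the SAP necessarily produces halved scores. The text does not support that. It does not say that only non-missing values are summed, as 16.1.1 does, so a programmer could equally treat the two-day sum as undefined and set the score to missing. This stands: halving is one of two readings.

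Third, the output diary form and the table shells are not in the documents. How a day without stool is coded, and whether a baseline form score exists, cannot be checked. This also stands, and it limits any statement about how often the problem would occur.

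A reader might also take the group-mean figures as an expected bias. They are not: q and m are chosen values.

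**Conclusion.** The point holds as a minor one. The formula in 18.8 is sound for the stool count when both days are recorded, and for the form score when both days are rated. For a visit with one rated day it yields either half the rating or no score, and the SAP does not say which. Neither outcome is a sensible average of the ratings that exist.

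The single-visit effect under the halving reading is exact: 6 becomes 3.0. Any shift in a group mean is illustrative only, because the documents do not give the frequency of one-rating visits or the mean score at them. Under that reading the visit score errs only downwards.

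The consequence is confined to one descriptive output variable. No hypothesis is tested, no PS endpoint is affected, and 18.8 also provides a listing.

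**What to change.** In 18.8 of the prospective SAP, give the two measures separate rules:

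- **Stool form score:** divide the sum of ratings by the number of days with a rating (1 or 2); set it to missing if neither day has one.
- **Number of stools per day:** divide by the number of days recorded. A documented day without stool counts as 0; an unrecorded day does not.

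State also that these rules, and not the weekly PS rule in 16.1.1, apply to the 48-hour output diary.

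The cost is one or two sentences and a small program change. Visits with both days recorded and rated keep their values. The downside is that a one-day value is noisier, and accepting 1 of 2 days (50%) is looser than the PS standard, where at most 2 of 7 days may be missing (5/7 = 71%).
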